The dislocated prosthesis is usually managed by a simple, closed reduction maneuver under general anesthesia with or without muscle relaxation, resulting in open surgical reduction rarely being needed (9-11). Time from admission to actual reduction often includes various steps (incl. several patient transfers between emergency units, radiology departments, operating theaters) which causes an unnecessarily long period of pain for the patient. In 2015, a fast-track system was introduced at Hvidovre Hospital on a trial basis for patients highly suspected for THA/HA dislocation (12). This resulted in a significant decrease in the time from arrival to reduction and overall time of hospitalization, without resulting in more complications. The study was retrospective and did not measure how patients experienced the change in practice.

A fast-track system must be specially designed for the local departments, due to differences in the logistical options from hospital to hospital. The purpose of this study is to design a fast-track pathway for patients referred to the University Hospital of Southern Denmark, Esbjerg, with high probability of having a dislocated hip prosthesis with the primary aim to reduce the time from arrival to reduction and the total hospitalization time. Secondary aims are to

- investigate whether quicker prosthesis reduction influences on hip function and quality of life afterwards
- reduce the pain experience immediately and in the long term
- increase patient satisfaction

without changing the overall complication rate and readmission/mortality

Methods:

Trial design

The study is designed as a prospective observational cohort trial, adhering to the STROBE guidelines (13). The present protocol will be registered at clinicaltrials.org and submitted for publication in an international journal.

Setting

The study is conducted at the University Hospital of Southern Denmark, Esbjerg, as a collaboration between the Department of Orthopedics, Department of Anesthesiology, Department of Radiology, and Department of Emergency.

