The goal for the new fast-track sedation pathway is a short deep sedation, according to the definition of level of sedation by ASA (14). This is for optimal patient comfort and success and with very low risk of aspiration (15, 16). The patient is sedated with Propofol 0,5-1 mg/kg and/or Esketamine 0,1-0,5 mg/kg. If a repeat dose is necessary, it is with Propofol 0,2 mg/kg and/or Esketamine 0,1-0,5 mg/kg (17, 18). Before sedation an intravenous line is placed with 1 L Ringer Acetate and the patient will receive a nasal cannula with an oxygen flow of 2-5 L/min. During the sedation the patient is monitored with a non-invasive blood pressure, saturation, respiratory rate, pulse and 3-point ECG and the nurse anesthetist and anesthesiologist will continuously observe the depth of sedation and respiratory drive. After the hip reduction, the patient is observed and monitored until the sedation has worn off and there is no risk of airway obstruction.

Outcomes

The *primary* outcome is time from arrival at the emergency entrance to prosthesis reduction.

The *secondary* outcomes are:

- a) total hospitalization time from arrival to discharge
- b) intra-operative complications (fracture, unsuccessful reduction, aspiration, need for mask ventilation and/or intubation, others)
- c) post-operative complications (cardiac, pulmonal, thrombo-embolic events, nerve damage, re-dislocation, others) during hospitalization
- d) 30 days re-admission
- e) 30- and 90-days mortality
- f) hip-related pain measured by a 10-digit numeric rating scale (NRS)
- g) patient-reported outcome (PRO) using the Hip disability and Osteoarthritis Outcome Score (HOOS), domains ¹⁾PAIN, ²⁾OTHER SYMPTOMS, ³⁾FUNCTION IN DAILY LIVING, AND ⁴⁾HIP-RELATED QUALITY OF LIFE (19)
- h) Health-related quality of life using the EQ-5D questionnaire (20)
- i) patient satisfaction
- j) time consumption by the involved staff (orthopedic, anesthetic, radiology staff etc.)
- k) total hospital costs during admission

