As the acute treatment has been performed when the patient is asked for consent, we apply for the use of the data acquired during the acute treatment of the patient, regardless of whether they choose to participate in the secondary part of the study regarding the patient-reported outcomes, in order to not prolong the study unnecessary. This includes the patient- and prosthesis-related factors, as this will be used to control for potential residual confounding.

Sample size

Study sample size are based on the primary outcome “Time from arrival at the emergency entrance to prosthesis reduction”, applying a formula for RCT studies with clinically superiority design (21). The null-hypothesis dictates no difference in time from arrival at the emergency entrance to prosthesis reduction for patients following the Standard Pathway or the Fast-Track Pathway.

$$N = 2 \times \left(\frac{z_{1-\alpha} + z_{1-\beta}}{\delta - \delta_0} \right)^2 \times s^2$$

N = no. of patients in each group

Alpha-value = 0,05 (5% risk of type-1 error)

Beta-value = 0,90 (10% risk of type-2 error)

Delta-value (estimated true value between the two groups) \approx 4 hours

Delta₀-value (estimated clinical acceptable difference between the two groups) \approx 3 hours

S-value (pooled standard deviation (SD) for both groups) \approx 2.5 hours

A review of 16 randomly selected patients that was admitted to the University of Southern Denmark, Esbjerg, with a dislocated THA from January 2018 to May 2022 revealed a mean time from arrival at the emergency entrance to prosthesis reduction at 6 hours (range 2.7 – 9.0 hours) with a standard deviation at 1.6 hours.

$$N = 2 \times \left(\frac{1,645 \times 1,28}{4 - 3} \right)^2 \times 2,5^2 \approx 53 \text{ patients in each group}$$

Based on a review of the surgical procedures performed during the period 01.02 – 31.08.2022, we expect to admit 5-6 patients per month with a dislocated THA or HA, and we expect an attendance rate of >90% based on the primary outcome. Therefore, we will include 53 patients + 15% ≈ 60 patients in each group, due to the risk that specific comorbidities will lead to exclusion from the Fast-Track pathway by the anesthetic staff. It is thus expected that a total of 120 patients will be adhered to one of the two treatment algorithms over the course of 24 months.

Blinding

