The patients are informed that consent gives the trial manager, sponsor and sponsor's representatives as well as any supervisory authority direct access to obtain information in the patient's medical record, etc., including electronic medical records, in order to see information about the subject's health, which is necessary as part of the implementation of the research project and for control purposes, including self-control, quality control and monitoring, which they are obliged to carry out.

Statistics

Mean values with standard deviation (SD) are given for normally distributed data, while median values with interquartile range (IQR) are given for skewed data. In case of normally distributed data, two-sample t-test is used. Mann-Whitney U-test is used to compare continuous nonparametric variables and chi-square test is used to compare categorical variables. STATA version 18 will be used for all statistical analyses.

Economy

The main investigator and initiator is [name], Ph.D., post.doc.

The study is conducted as a collaboration between the Department of Orthopedics, Department of Anesthesiology, Department of Radiology, and Department of Emergency Medicine, University Hospital of Southern Denmark, Esbjerg. There are no special economics involved in the study between the departments, as the study is carried out as a part of normal daily, acute activity.

Vestjysk Orthopedic Fund will be applied for covering expenses to hardware (computer, Ipad etc.)

The Region of Southern Denmark's Research Fund will be applied for covering salary to a dedicated study nurse.

Grants are administered via an account that is subject to public audit.

There are no conflicts of interest.

Ethics

Permission to store and handle data is obtained upon application to the Region of Southern Denmark's internal register (24/34681). The Danish Law of data protection is observed.

The regional ethics committee has been applied for permission to conduct the study under special circumstances as acute research without the possibility of obtaining informed consent from the

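### The aim of unchanged complications, readmission and mortality is paired only with a chi-square test of difference, which cannot show that these rates are unchanged

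*Protocol*

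**What the plan says.** - **Aims (Protocol, end of Background).** The primary and secondary aims are followed by a condition: they are to be reached "without changing the overall complication rate and readmission/mortality".
- **Outcomes (Protocol, Outcomes, secondary b to e).** The condition corresponds to four outcomes. Item b) collects problems during the procedure, such as a fracture, a failed reduction or a need for airway support. Item c) collects later problems in the same stay, among them a new dislocation. Item d) is readmission within a month, and item e) is listed as "30- and 90-days mortality". No expected rate is given for any of them.
- **Analysis (Protocol, Statistics).** The section is one short paragraph. For outcomes of this type it says only that a "chi-square test is used to compare categorical variables". It names no interval and no acceptable difference.
- **Size (Protocol, Sample size).** "Study sample size are based on the primary outcome", which is time from arrival to reduction. The result is that "we will include 53 patients + 15% ≈ 60 patients in each group". A margin (3 hours) is stated for time; none is stated for safety.

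**The concern.** A chi-square test takes equal rates as its null hypothesis. It can give evidence that rates differ. If it does not reject, it leaves open every difference that the data are too few to rule out. The aim asks for the opposite kind of statement, that rates have not changed by an amount that matters, and that needs an estimate with an interval, or a margin. The stated method therefore does not answer the stated aim.

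The Fast-track pathway replaces general anaesthesia in theatre with sedation in the trauma room, and the gain in time is to be weighed against unchanged safety. The Ethics section already expects Fast-track to carry no greater risk and perhaps less. If the report follows Statistics as written, safety will rest on a list of p-values. At this sample size a large p-value is compatible both with no change and with a substantial excess, and the reader could not tell which.

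**Working it through.** **Inputs from the protocol.** About 60 patients per group (Sample size); a chi-square test (Statistics). The protocol's inflation step is 53 × 1.15 = 60.95, which it rounds to about 60. The 53 itself does not follow exactly from the printed expression: 2 × (1.645 × 1.28)² × 2.5² = 55.4. That is a separate matter, and this check simply takes the planned 60.

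**Assumed inputs.** The baseline event rate is not in the protocol, so a range of 2% to 25% is shown. The test is taken as two-sided at 5% without continuity correction. Admissions are treated as independent, although a patient may enter more than once.

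**Step 1: power to detect a doubling.** Let X_S ~ Bin(60, p) and X_F ~ Bin(60, 2p). Add up the probability of every pair (x_S, x_F) for which |z| > 1.96, where z = (x_F − x_S)/60 ÷ √[p̄(1 − p̄) × 2/60] and p̄ = (x_S + x_F)/120. This z² is the chi-square statistic.

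| Standard → Fast-track (assumed) | Expected events in 60 + 60 | Power | Chance of missing it |
|---|---|---|---|
| 2% → 4% | 1.2 + 2.4 | 7% | 93% |
| 5% → 10% | 3 + 6 | 17% | 83% |
| 10% → 20% | 6 + 12 | 33% | 67% |
| 15% → 30% | 9 + 18 | 51% | 49% |
| 20% → 40% | 12 + 24 | 68% | 32% |
| 25% → 50% | 15 + 30 | 82% | 18% |

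A tripling from 5% to 15% is detected with 46% power.

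**Step 2: what an equal result would establish.** Suppose 3/60 (5%) in each group. The Wilson 95% limits for 3/60 are 1.71% and 13.70%. Newcombe's limits for the difference of zero are ±√[(0.1370 − 0.05)² + (0.05 − 0.0171)²] = ±√(0.00757 + 0.00108) = ±0.093. Identical counts thus leave -9.3 to +9.3 points.

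**Step 3: what a non-significant result could hide.** Suppose 3/60 under Standard and 6/60 under Fast-track, an observed doubling.
- Chi-square = 0.05² ÷ (0.075 × 0.925 × 2/60) = 0.0025/0.0023125 = 1.08, so p = 0.30.
- The Wilson limits for 6/60 are 4.66% and 20.15%.
- Upper limit: 0.05 + √[(0.2015 − 0.10)² + (0.05 − 0.0171)²] = 0.05 + 0.107 = 0.157.
- Lower limit: 0.05 − √[(0.10 − 0.0466)² + (0.1370 − 0.05)²] = 0.05 − 0.102 = -0.052.

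The p-value of 0.30 belongs to an interval of -5.2 to +15.7 points. Only the interval shows that an excess of 15 points has not been ruled out.

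**Step 4: no events at all.** With 0/60, the upper limit of the exact two-sided 95% interval for that group's rate is 1 − 0.025^(1/60) = 6.0%.

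**The case against.** **No decision rule is quoted.** A reader might infer that the protocol intends to take a non-significant test as proof of unchanged safety. It does not say so. The condition is a clause attached to the aims, not a formal equivalence hypothesis; the only null hypothesis stated concerns time; these outcomes are secondary; and the protocol commits to publishing inconclusive results. This stands. The misreading is a risk that the plan leaves open, not a rule that it sets.

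**Rarity is assumed.** A reader might also infer that these events are rare, or that a non-significant result is to be expected whenever complications double. The protocol supports neither. It gives no rates, and the outcome groups are broad: they include failed reduction, mask ventilation, re-dislocation and an open category of others. At a 25% baseline a doubling is found with 82% power. This limits the size of the problem, but the mismatch between aim and test does not depend on the event rate.

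**Sparse counts.** It is tempting to add that chi-square p-values are unreliable here and that an exact test is needed. The figures do not support that. With true rates of 3% and 5% in both groups, the chi-square test rejects in 3.5% and 4.6% of studies, so its error rate is not inflated. Fisher's test would make harm harder to see: its power for 5% to 10% is 8.8%, against 17.4%.

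**It may be in a statistical analysis plan.** Intervals are often specified there, and naming a chi-square test does not forbid them. But the protocol states both an aim and a method, and the two do not fit. An analysis plan could add intervals; the protocol text would still need to agree with it.

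**Low power for secondary safety outcomes is ordinary.** Agreed. It is not in itself an error, and no larger study is asked for.

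**Conclusion.** The point holds in this form: the aim of unchanged complications, readmission and mortality has no matching analysis, because a test of difference without a margin or interval cannot support it. That much is a matter of logic and needs no assumed rate.

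The size of the problem does rest on assumed rates. At 60 independent admissions per group and baselines up to about 10%, a true doubling would be missed in 67% to 93% of such studies. At 15% it is close to an even chance, and at 25% it would usually be found. The interval of ±9.3 points for 3/60 against 3/60 shows how little even an equal result would exclude.

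The change should be made. The primary analysis of time to reduction is not affected.

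**What to change.** In the Statistics section of the protocol, add one paragraph for secondary outcomes b) to e):

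- The main result for each outcome is the count and percentage per pathway and the risk difference (Fast-track minus Standard) with a 95% Newcombe confidence interval.
- Safety is described as an estimate. A non-significant test is not evidence that rates are unchanged.
- The conclusion is worded by the upper confidence limit, in the form: an excess above x percentage points is excluded.

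The chi-square test may remain as a supplement, and no exact test is needed. Because patients can enter more than once, say in the same paragraph that these intervals follow the protocol's promised handling of repeat admissions.

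The cost is one paragraph and a small amount of extra output, with no added patients or data. The real price is that the safety conclusion will read less favourably than a row of non-significant p-values would.
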